1. BACKGROUND AND SIGNIFICANCE

1.1 Oral lichen planus

Oral lichen planus (OLP) is a common benign, chronic immune-mediated inflammatory condition that occurs in 1 to 2% of adults¹. Middle-aged women are twice as likely to be affected as men. OLP may be associated with a variety of systemic and local conditions and medication use such as thiazide diuretics, angiotensin converting enzyme (ACE) inhibitors, beta blockers, gold salts, sulfasalazine, sulfonyleureas and penicillamine. Biologic agents such as tumor necrosis factor (TNF) alpha inhibitors may also cause lichen planus-like eruptions². Amalgam and composite restorations may cause localized contact lichenoid hypersensitivity reactions possibly to mercury and formaldehyde.

OLP can affect any mucosal surface, and most commonly affects the buccal mucosa and tongue bilaterally. OLP can present with three distinct forms: reticular/keratotic, erosive/erythematous, and ulcerative forms. The reticular/keratotic form, characterized by Wickham striae, is the most common form and is often asymptomatic. Occasionally patients will report discomfort and describe the buccal mucosa as “rough,” “thick,” or “tight”. The erosive/erythematous form typically presents as desquamative gingivitis. Patients may complain of discomfort while eating acidic, spicy or crunchy food. The ulcerative form is the most severe and presents as shallow ulcerations that have a yellow fibrin membrane on the surface. Often, there is a combination of the three forms at different sites, or at different times. Most patients exhibit a characteristic bilateral and symmetric distribution of lesions, typically involving the buccal mucosa, dorsum and ventral surfaces of the tongue and/or gingiva.

The diagnosis of oral lichen planus is based primarily on clinical characteristics, although biopsy may be indicated when the presentation is not typical (e.g. unilateral presentation, or lack of reticulation features)^{3,4}. Histopathological examination demonstrates a lymphocytic band of variable thickness at the interface and degeneration or loss of the basal cell layer.

1.1.1 Management of oral lichen planus

Available therapies for OLP are not curative, but are aimed at managing symptoms through the reduction of inflammation. The mainstay of therapy remains use of topical corticosteroids which can be delivered in various vehicles including gels and solutions^{1,5,6}. A response to treatment with midpotency corticosteroids (e.g., triamcinolone acetonide 0.1%), potent fluorinated corticosteroids (e.g., fluocinolone acetonide 0.1% and fluocinonide 0.05%), and super- potent halogenated corticosteroids (e.g., clobetasol propionate 0.05%), has been reported in 30–100% of treated individuals⁷⁻¹².

One of the challenges in applying topical corticosteroids is the lack of adherence to the oral mucosa for an adequate duration for the medication to be locally absorbed. Numerous obstacles are encountered when a topical steroid is prescribed to treat OLP, including the presence of saliva, changes in taste, poor tissue penetration, enzymatic degradation, and the need for frequent dosing, all of which may negatively affect patient compliance¹³. One approach to develop more efficacious and safer therapies could be inflammation-targeting drug delivery to achieve high drug concentrations locally at the site of inflammation with minimal exposure of healthy or distant tissues.

Use of topical steroids for oral lichen planus may lead to the development of secondary candidiasis in 11-47% of patients, which requires antifungal therapy^{10,14,15}. Antifungal drug therapy, such as fluconazole has been showed to be an effective prophylaxis measure to prevent oral candidiasis

CONFIDENTIAL

This document is confidential. Do not disclose or use except as authorized.

infection¹⁶⁻¹⁸. Although there are some reports of systemic absorption and adrenal suppression from super-potent topical steroids in the treatment of chronic dermatologic disorders, adrenal suppression is uncommon even in long-term oral application of topical corticosteroids such as fluocinonide and clobetasol¹⁹⁻²¹. Systemic absorption from topical steroids has been reported and it is thought that absorption of small amounts through the oral mucosa can take place, but clinical experience and laboratory studies have shown this not to be of clinical significance in almost all cases²². Gonzalez-Moles et al. reported two cases of moon facies (2/30) and two cases of hirsutism (2/30) secondary to long-term use (> 4 weeks) of clobetasol 0.05% solution for the treatment of oral erosive lesions. All cases resolved upon discontinuation of the medication and/or reduction in frequency of administration. Other side effects reported include nausea, mucosal atrophy, xerostomia, halitosis and delayed healing^{22,23}.

1.2 Dexamethasone solution for oral lichen planus

The efficacy of dexamethasone solution has been well described in several clinical trials. Rhodus et al. conducted a prospective controlled clinical trial to test the efficacy of dexamethasone solution in 13 patients with oral erosive-ulcerative lichen planus²⁴. Patients were instructed to rinse with 5 ml of dexamethasone 0.1% solution for 3 min and then to expectorate. Subjective symptomatology (pain and/or discomfort) was recorded on a 100 mm visual analogue scale (VAS) at first visit and at 6 week follow up. Patients experienced significant subjective improvement in symptoms following the dexamethasone treatment (VAS score pre-treatment: 6.7 ± 1.4 ; VAS score post-treatment: 2.3 ± 0.6). Hambly et al. conducted a single-blinded, cross-over pilot trial in nine patients to compare the efficacy of compounded dexamethasone solution for OLP²⁵. Patients were instructed to rinse with 2 ml of dexamethasone 0.5 mg/2 mL compounded as a solution or one 0.5 mg tablet crushed and mixed with 20 ml water three times per day for 3 weeks. All patients were instructed to rinse and hold the medication in their mouths for at least 2–3 minutes and then expectorate. Participants were evaluated at weeks 0, 3, 4, and 7. Symptoms were recorded with a 100-mm VAS; other assessments included the Treatment Satisfaction Questionnaire for Medication-9, comparisons of clinical photographs, and self-assessment via patient daily diary entries to record compliance with each dose. Results showed the compounded dexamethasone solution to be more effective compared to 0.5 mg dexamethasone tablet crushed and mixed with 20 ml water in terms of compliance, patient-perceived faster onset of action, and improved symptom relief.

1.3 Mucolox™

Mucolox™ is a mucoadhesive polymer gel that can be used in pharmaceutical compounding for the management of diseases and conditions of the oral mucosa including oral mucositis, and mouth ulcers^{26,27}. The safety and toxicological profile of Mucolox™ was evaluated in vitro and compared to Triton X-100 (positive control) and distilled water (negative control), using a 3-dimensional model of the human oral mucosa. Results showed that Mucolox™ can bind to tissues six times longer than Triton X-100 (before 50% cell viability) therefore offering increased retention of medication at the site of action. Additionally, at 4.5 hours, the difference in percent cell viability between Mucolox™ and distilled water was not significant, making it a safe water-soluble mucosal delivery system.

CONFIDENTIAL

This document is confidential. Do not disclose or use except as authorized.

1.4 Significance

There is a significant unmet need for optimized topical therapies for oral lichen planus. Topical steroid therapy is considered the first line of treatment for oral lichen planus with current treatment regimens requiring multiple application or rinses daily^{24,28,29}. Although topical steroid therapy can be successful for most patients, the treatment schedule can be challenging to maintain. There is therefore considerable interest in developing new and more effective therapies that require less frequent applications. The possibility of having a treatment agent that is safe, easy to use, and cost effective, with potentially greater efficacy than the current standard of care available topical steroid solutions would be ideal. Using Mucolox™ as a vehicle to deliver topical dexamethasone to the oral mucosa has the potential to effectively prolong contact time between the medication and mucosa, leading to improved clinical outcomes due to the need for less frequent application. This technology would help to more efficiently achieve high drug concentrations locally. By possibly shortening the frequency and time of topical therapy and improving patient compliance, this may translate to greater therapeutic benefit.

2. SPECIFIC AIMS

The objective of this single center, 4-week, open label randomized, phase II study is to evaluate and characterize the tolerability and clinical effectiveness of dexamethasone 0.5mg/5ml solution in a mucoadhesive vehicle (Mucolox™) for the treatment of oral lichen planus. Completion of this study will establish important data on the efficacy of topical steroid therapy when combined with a carrier and delivery system such as Mucolox™. If significant benefits are noted, this approach could be applied to the management of other oral mucosal immune-mediated conditions, such as graft-versus-host disease and mucous membrane pemphigoid.

2.1 Study Design

This is a single center, 4-week, open label randomized, phase II study. Randomization will be conducted by the BWH Investigational Pharmacy. The study period will be four weeks, which based on previous studies should be an adequate period to assess significant clinical improvement. Subjects will be evaluated clinically at baseline before starting treatment and at the end of the four-week period, for a total of two visits. Subjects will be randomized to either compound dexamethasone in Mucolox™ or dexamethasone only. Subjects will return for evaluation after four weeks at which time the primary end-points will be assessed.

2.2 Primary Objective

The primary objective of this study is to determine the clinical efficacy and tolerability of compound dexamethasone at 0.5 mg/5 mL in Mucolox™ for the treatment of oral lichen planus as measured by a reduction in oral symptoms between patients treated with commercial dexamethasone 0.5mg/5ml solution in Mucolox™ (group A) and patients treated with topical dexamethasone 0.5mg/5ml solution only (group B).

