2.3 Secondary Objective

CONFIDENTIAL

This document is confidential. Do not disclose or use except as authorized.

The secondary objectives are:

- To determine the clinical improvement in clinician-reported outcome measures achieved by treatment with topical compound dexamethasone at 0.5 mg/5 mL in Mucolox™ compared to dexamethasone 0.5mg/5ml solution alone.
- To assess the tolerability of oral lichen planus as measured with the chronic oral mucosal diseases quality of life questionnaire (COMDQLQ).

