2.4 Hypothesis

Dexamethasone solution (0.5mg/5ml) in Mucolox™ when swished for 5 minutes and expectorated three times daily, is *well-tolerated* and *more effective* than dexamethasone solution (0.5 mg/5 mL) alone in the management of oral lichen planus.

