6.5 Analysis of Secondary Endpoints

Oral health related quality of life will be assessed before and after topical therapy using the 24-item Chronic Oral Mucosal Diseases Quality of Life Questionnaire (COMDQLQ; see Appendix) instrument that measures subject's perceptions of the impact of oral conditions on their well-being. The COMDQLQ scores will be summarized descriptively for each arm at pre-treatment, post-treatment, and pre-to-post treatment change. The pre-to-post treatment change for each item and for all items combined will be assessed within each arm using either paired t test or Wilcoxon-signed-rank test depending on its distribution. In addition, each question will be dichotomized and classified as 'response' if the answer is 'not at all', or 'slightly' to a question such as "how isolated do you feel as a

CONFIDENTIAL

This document is confidential. Do not disclose or use except as authorized.

result of this oral condition”, and pre-to-post treatment improvement will be assessed using McNemar’s test within each arm.

In order to evaluate the clinical improvement in clinician-reported outcome measures for oral lichen planus, REU scores within the compound dexamethasone solution in Mucolox™ group (Arm A) will be compared to that in the dexamethasone solution only group (Arm B). The REU scores will be summarized descriptively for each arm at pre-treatment, post-treatment, and pre-to-post treatment change. The pre-to-post treatment change will be compared between the arms using either student’s t-test or Mann–Whitney test, depending on the distribution of the data.

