- 0 = Not at all
- 1 = Slightly
- 2 = Moderately
- 3 = Quite a bit
- 4 = Extremely

CONFIDENTIAL

This document is confidential. Do not disclose or use except as authorized.

OBJECTIVE DATA (REU score)

Site	Reticular area			Erythematous area			Ulcerative area				
	0	1		0	1	2	3	0	1	2	3
Upper/lower labial mucosa	0	1		0	1	2	3	0	1	2	3
Right buccal mucosa	0	1		0	1	2	3	0	1	2	3
Left buccal mucosa	0	1		0	1	2	3	0	1	2	3
Dorsal tongue	0	1		0	1	2	3	0	1	2	3
Ventral tongue	0	1		0	1	2	3	0	1	2	3
Floor of mouth	0	1		0	1	2	3	0	1	2	3
Hard palate mucosa	0	1		0	1	2	3	0	1	2	3
Soft palate/tonsillar pillars	0	1		0	1	2	3	0	1	2	3
Maxillary gingiva	0	1		0	1	2	3	0	1	2	3
Mandibular gingiva	0	1		0	1	2	3	0	1	2	3
Total											

(R: 0 = not present, 1 = present; E & U: 0 = not present, 1 = <1cm², 2 = 1 - 3cm², 3 = >3cm²)

Total Score:

Total Weighted Score:

PHOTOGRAPHS TAKEN (circle): YES NO

CONFIDENTIAL

This document is confidential. Do not disclose or use except as authorized.

DEXAMETHASONE RINSE AND MUCOLOX™ FOR THE TREATMENT OF ORAL LICHEN PLANUS

VISIT #2

Subject Name _____

Medical Record Number _____

Date of Visit _____

[figure not shown]
[figure not shown]
SUBJECTIVE DATA (Over last one week unless specified)

MUCOSAL PATHOLOGY

1. Does your mouth hurt now? Y/N

2. Does it hurt to swallow food or drink? Y/N

3. How would you rate your worst mouth sensitivity over the last week?

No sensitivity

Worst sensitivity

4. Do you avoid any foods because they make your mouth hurt?

- 0 = Not at all
- 1 = Slightly
- 2 = Moderately
- 3 = Quite a bit
- 4 = Extremely

If “yes”, what types of foods?

[figure not shown]
[figure not shown]
- a. Spicy foods
- b. Acidic foods
- c. Salty foods

CONFIDENTIAL

This document is confidential. Do not disclose or use except as authorized.

- d. Hard/crunchy/crusty foods
- e. Other:

5. Do you feel that your oral intake (what you eat) is limited by your oral condition? Y/N

Not limited at all

Severely limited

Score: _____

[figure not shown]
[figure not shown]
If “Yes”, how limited do you feel it is?

- a. Partial limitation
- b. Severe limitation

6. Have you been bothered by ulcers in the mouth?

- 0 = Not at all
- 1 = Slightly
- 2 = Moderately
- 3 = Quite a bit
- 4 = Extremely

7. Rate your level of comfort while rinsing with the topical therapy:

Not uncomfortable at all

[figure not shown]
[figure not shown]
Very uncomfortable

Score: _____

CONFIDENTIAL

This document is confidential. Do not disclose or use except as authorized.

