8. Rate the taste of the topical treatment:

[figure not shown]
[figure not shown]

Very good taste

Very bad taste

Score: _____

9. Rate how your mouth feels since starting topical therapy:

Mouth feels much better

Mouth feels much worse

Score: _____

10. Overall, since beginning topical therapy, my mouth is: (Check one)

- Very much better
- Moderately better
- A little better
- About the same
- A little worse
- Moderately worse
- Very much worse

CONFIDENTIAL

This document is confidential. Do not disclose or use except as authorized.

OBJECTIVE DATA

Site	Reticular area			Erythematous area			Ulcerative area			
	0	1	0	1	2	3	0	1	2	3
Upper/lower labial mucosa	0	1	0	1	2	3	0	1	2	3
Right buccal mucosa	0	1	0	1	2	3	0	1	2	3
Left buccal mucosa	0	1	0	1	2	3	0	1	2	3
Dorsal tongue	0	1	0	1	2	3	0	1	2	3
Ventral tongue	0	1	0	1	2	3	0	1	2	3
Floor of mouth	0	1	0	1	2	3	0	1	2	3
Hard palate mucosa	0	1	0	1	2	3	0	1	2	3
Soft palate/tonsillar pillars	0	1	0	1	2	3	0	1	2	3
Maxillary gingiva	0	1	0	1	2	3	0	1	2	3
Mandibular gingiva	0	1	0	1	2	3	0	1	2	3
Total										

(R: 0 = not present, 1 = present; E & U: 0 = not present, 1 = <1cm², 2 = 1 - 3cm², 3 = >3cm²)

Total Score:

Total Weighted Score:

PHOTOGRAPHS TAKEN (circle): YES NO

CONFIDENTIAL

This document is confidential. Do not disclose or use except as authorized.

COMDQLQ

	Not at all (0)	Slightly (1)	Moderately (2)	Considerably (3)	Extremely (4)
Pain and functional limitation					
How much do certain types of food/drink cause you discomfort (spicy food, acidic food)?					
How much does your oral condition cause you to limit the types of food/ drinks you consume?					
How much do certain food textures cause you discomfort (rough food, crusty food)?					
How much does your oral condition cause you to limit the textures of the food you consume?					
How much does the temperature of certain foods/drinks cause you discomfort?					
How much does your oral condition cause you to limit the temperature of the foods/ drinks you consume?					
How much does your oral condition lead to discomfort when carrying out your daily oral hygiene routine (brushing, flossing, mouthwash usage)?					
How much does your oral condition cause you to limit your daily oral hygiene routine (brushing, flossing, mouthwash usage)?					
How much does your oral condition lead to discomfort when wearing a denture (false teeth)?					
Medication and treatment					

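### Tolerability is in the primary objective and the hypothesis, but the objectives measure it by symptom relief and a quality-of-life score, and Section 6 gives no between-arm summary of the tolerability data collected

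*Combined protocol and SAP*

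**What the plan says.** - **Objectives and hypothesis.** Section 2.2 aims to "determine the clinical efficacy and tolerability of compound dexamethasone at 0.5 mg/5 mL" in Mucolox, and the same sentence supplies one yardstick: "as measured by a reduction in oral symptoms between patients treated with commercial dexamethasone 0.5mg/5ml solution". Section 6.1 repeats efficacy and tolerability as the joint primary objective. Section 2.4 states that the Mucolox rinse "is *well-tolerated* and *more effective* than dexamethasone solution (0.5 mg/5 mL) alone".
- **Secondary objective.** Section 2.3 reads "To assess the tolerability of oral lichen planus as measured with the chronic oral mucosal diseases quality of life questionnaire (COMDQLQ". Read literally, this is tolerability of the disease, not of the rinse.
- **Analysis.** Section 6.4 compares the change in sensitivity score between arms. Section 6.5 compares the REU change between arms. The COMDQLQ change "will be assessed within each arm using either paired t test or Wilcoxon-signed-rank test", and its dichotomised items are tested by McNemar's test, also within arm.
- **Data collected.** The Visit #2 CRF (Appendix 4) has item 7, "Rate your level of comfort while rinsing with the topical therapy"; item 8, "Rate the taste of the topical treatment"; and item 10, "Overall, since beginning topical therapy, my mouth is". Diaries record adverse effects (5.2, 5.3). Stopping because the rinse cannot be tolerated is an off-therapy reason that must be documented (5.6). Adverse events are graded and attributed (10.5).
- **Stated intention.** Section 5.1.3 says that tolerability, compliance and the patient's global assessment will be evaluated, without naming a variable, summary or criterion. Section 6.6 mentions a toxicity report, and 6.6.1 has a study-wide toxicity stop.

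**The concern.** Reduction in symptoms is an efficacy measure. A rinse can relieve lichen planus and still burn or taste bad, so a good result on the sensitivity score says little about how the rinse was tolerated. The COMDQLQ asks mostly about the disease and its effect on daily life, and a within-arm change cannot show whether one vehicle is better tolerated than the other.

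The symptom comparison is also partly selected on tolerance. Under Section 6.6, patients who under-use the rinse beyond a set limit are unevaluable for the primary endpoint and are replaced. Someone who cut back because the rinse was unpleasant could therefore drop out of the comparison that 2.2 offers as the measure of tolerability.

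Drug, concentration, volume, rinse time and frequency are the same in both arms in the Section 5.2 table, so the vehicle is the planned difference. Section 1.1.1 lists taste changes among the obstacles to compliance, and Section 1.4 argues for Mucolox partly on compliance. Comfort and taste by arm are thus a direct randomised comparison of what the trial varies. Without a specified analysis, a claim of good tolerability could rest on symptom relief, or on measures picked after open-label data have been seen.

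**Working it through.** **1. Objective against analysis**

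| Element | Assigned to tolerability? | Analysis in Section 6 |
|---|---|---|
| Sensitivity score | Yes, by 2.2 | Between arms (6.4) |
| COMDQLQ | Yes, by 2.3; quality of life in 6.1 and 6.5 | Within arm only (6.5) |
| Item 7, comfort | Not by the objectives | None specified |
| Item 8, taste | Not by the objectives | None specified |
| Stopping for intolerance | Not by the objectives | None specified |
| Adverse events | Not by the objectives | Toxicity report and stopping rule; no summary by arm |
| Item 10, global rating | No (efficacy) | None specified |

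The measures named for tolerability do not suit it, and those that suit it have no specified comparison.

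**2. The plan's own sample size**

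Inputs from 6.2: difference 2.0, SD 1.4, two-sided alpha 0.05, power at least 80%, 5% loss, 12 per arm.

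- Normal approximation: 2 × (1.960 + 0.842)² × 1.4² / 2.0² = 7.7, so 8 per arm.
- Two-sample t-test: 9 per arm; 9 / 0.95 = 9.5, so 10 after loss.
- Power of the t-test is 0.917 at 12 per arm and 0.890 at 11.

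The stated 12 per arm meets the power claim for the efficacy endpoint. It was not derived for tolerability.

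**3. What a between-arm estimate of comfort or taste could show**

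Half-width of the 95% CI = t(0.975, 2n − 2) × SD × √(2/n).

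- n = 12: 2.074 × √(2/12) = 0.847 SD
- n = 11: 2.086 × √(2/11) = 0.889 SD

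The documents give no SD for items 7 and 8, and their scale graphics are not shown. A 0-10 scale and the SDs below are assumptions; 1.4 is borrowed from the sensitivity change in 6.2.

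| Assumed SD | Half-width, n = 12 | Half-width, n = 11 | Power for 2 points, n = 12 |
|---|---|---|---|
| 1.4 | 1.19 | 1.25 | 0.92 |
| 2 | 1.69 | 1.78 | 0.65 |
| 3 | 2.54 | 2.67 | 0.35 |

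At 12 per arm, 80% power needs a difference of 1.20 SD. This supports estimation rather than a powered test.

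**4. Zero intolerant patients in one arm**

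Exact two-sided 95% upper limit for 0 of 12: 1 − 0.025^(1/12) = 0.265, or 26.5%.

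**5. Whether the toxicity stop fills the gap**

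Section 6.6.1 ends the study at 3 or more patients with grade III-IV treatment-related toxicity. With 24 treated, P(X ≥ 3) = 1 − Σ(k = 0 to 2) C(24, k) pᵏ(1 − p)^(24 − k), which is 0.12, 0.44 and 0.89 at assumed true rates of 5%, 10% and 20%. The rule pools the arms and counts only severe events, so it neither compares the vehicles nor defines good tolerability.

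**The case against.** A reader might infer that tolerability is never measured or never analysed. The documents do not support that. Section 5.1.3 says it will be evaluated and lists it apart from the symptom scores. Diary adverse effects, documented intolerance, graded adverse events and a toxicity report that keeps non-compliant patients are all provided for. What is missing is the specification: which variables, summarised how, and compared between arms or not.

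A reader might also infer that the COMDQLQ says nothing about the rinse. That goes too far as well. Its medication domain asks about satisfaction with treatment, worry over side effects and the burden of using it, and 6.5 tests each item. But these are a few items in one domain, are also asked at baseline before study drug, and are tested only within arm, so they do not compare the vehicles.

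It can fairly be said that the wording in 2.3 looks like a slip that 6.1 and 6.5 do not repeat, and that well tolerated in 2.4 may be a descriptive claim, with only efficacy comparative. Descriptive reporting would be defensible in 24 patients. Even so, the plan specifies no descriptive summary of comfort or taste, and 2.2 still ties tolerability to symptom relief.

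Finally, the interval widths describe a small trial, not this defect. They would be the same before and after the change. They show how cautiously the results must be worded.

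**Conclusion.** The point holds. Tolerability is one of two parts of the primary objective and of the hypothesis, and the measures the objectives assign to it are an efficacy score and a quality-of-life score. The collected data that address tolerance of the rinse have no between-arm summary in Section 6, nor does the global rating.

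The consequence lies in what can be claimed about tolerability. It would be wrong to infer that the primary result is compromised: Sections 2.5, 6.1 and 6.4 make sensitivity change the primary endpoint with one between-arm test, and that test is untouched.

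Any tolerability estimate will be imprecise: a half-width of about 0.85 SD at 12 per arm, or 1.7 to 2.5 points on an assumed 0-10 scale with assumed SD 2 to 3, and an upper limit of 26.5% when 0 of 12 have an event. An unqualified statement that the rinse is well tolerated would therefore mislead even if no problem were seen. The trial is also open label, so comfort and taste ratings of a known vehicle are open to expectation bias. This should be corrected, but it does not threaten the trial.

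**What to change.** 1. **Section 2.2:** separate tolerability from symptom reduction, leaving symptom reduction as the measure of efficacy only.
2. **Section 2.3:** say that the COMDQLQ measures oral health related quality of life, as 6.1 and 6.5 already do. In 6.5, compare its change between arms, as is planned for the REU score.
3. **Section 6, new paragraph:** define tolerability as Visit #2 items 7 and 8, stopping the rinse because it cannot be tolerated, and treatment-related adverse events. Analyse all treated patients with data, including those unevaluable for the primary endpoint.
4. **Reporting:** give each measure by arm, with a between-arm difference and 95% CI. Label this as estimation, not a powered test, and use an interval method for proportions that copes with zero counts.
5. **Item 10:** compare between arms as supportive efficacy, not tolerability.
6. **Limits to state:** expectation bias in open-label comfort and taste ratings, and the low precision shown above.

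The cost is revised objective wording and a short analysis paragraph. No new visits, forms, data or patients are needed.
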